## 8 EFFICACY ANALYSES

Missing efficacy data will be imputed as described in [Section 4.2.1](#) prior to reporting. As a sensitivity analysis, summaries will be repeated based on non-imputed (OC) data for the following variables:

- ACR20, ACR50 and ACR70 response relative to PA0008 Baseline at each visit in PA0009.
- PASI75, PASI90 and PASI100 response relative to PA0008 Baseline at each visit in PA0009.
- MDA at each visit in PA0009.
- Change from PA0008 Baseline in MASES at each visit in PA0009.
- Change from PA0008 Baseline in LDI at each visit in PA0009.

A further sensitivity analysis will be performed for ACR20, ACR50 and ACR70, PASI75, PASI90 and PASI100 responses relative to PA0008 Baseline at each visit. The response endpoint will be re-derived and summarized based on the mean value (across multiple imputations) of the ACR component scores or PASI total score after imputation for missing data.

Efficacy variables will be summarized and listed (including individual raw data and derived domain and total scores, where applicable) for the FAS. Summaries of MASES will be restricted to subjects with a MASES  $>0$  at PA0008 Baseline, of LDI will be restricted to subjects with a LDI  $>0$  at PA0008 Baseline, and of PASI responses will be restricted to subjects with a BSA affected by psoriasis of  $\geq 3\%$  at PA0008 Baseline. Maintenance of response summaries will be restricted to subjects with a response at PA0008 Week 12 for the specific endpoint (where response at PA0008 Week 12 is taken directly from the PA0008 datasets).

Responder variables (eg, ACR20 response) will be derived relative to the PA0008 Baseline and summarized using n and percentage at each visit, by treatment group at completion of PA0008 and overall.

Maintenance of response will be assessed for ACR20, ACR50, ACR70, PASI75, PASI90 and PASI100. The responses will be derived relative to PA0008 Baseline and summarized using n and percentage at each post-PA0008 Baseline visit, by treatment sequence across PA0008 and PA0009. These summaries will therefore include PA0008 Week 2, 4, 8, 12, 16 (for ACR only), 20 (for ACR only), 24, and 36 and PA0009 EV [PA0008 Week 48], Week 12, 24, 36, 48, 60, 72, 84, 96, 100, and 104, for subjects who were responders at PA0008 Week 12.

Absolute and change from PA0008 Baseline for all continuous efficacy variables will be summarized descriptively by visit, by treatment group at completion of PA0008, and overall.

In the event that the MI model fails to converge or will not run for other reasons, alternative approaches may be considered as described in [Section 4.2.1](#) and additional outputs will be provided. The planned MI tables will be retained in the final delivery outputs with the following text included in the table body: 'Multiple imputation procedure was not possible to perform due to insufficient data and/or data distribution issues'.

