- The  $m$  datasets are summarized.
- The results of the  $m$  summaries are combined into a single result.

The MI method will be applied as follows:

### Step 1

- Create a data set, sorted by treatment group at completion of PA0008, of subjects with observed values and missing values needing imputation. Missing values will be separated into non-monotone (ie, intermittent missing values between completed assessments) and monotone (ie, missing values after the subject dropped out). The procedure will sequentially estimate an imputation model for the efficacy variable at each post-PA0008 Baseline visit where efficacy variables are collected, with PA0008 Baseline, geographic region, and past TNF inhibitor exposure (as collected on the eCRF in PA0008 for past anti-TNF exposure) as covariates, separately for each treatment group at the completion of PA0008.
- Intermittent missing data will be imputed by draws from the imputation model using the Markov-Chain Monte Carlo (MCMC) method with multiple chains and monotone imputing. A total number of imputations will be 100. The seed used for these imputations will be 2017.

Note: All MI procedures described in this SAP will use the same seed.

- The post-PA0008 Baseline values will be specified in chronological order in the imputation model so that the SAS® PROC MI imputes variables from left to right. If a PA0008 Baseline raw value is missing, the study participant will be excluded. The imputation model based on the MCMC method will only allow multivariate normal variables as predictors. Therefore, past TNF inhibitor exposure and geographic region will be re-coded as indicator variables. For past TNF exposure, this will be 0 for no past exposure and 1 for past TNF exposure. Similarly, for region, this will be 1 for subjects from Europe and 0 for all other subjects. The order for the covariates in the model will be as follows: region indicator variable (Europe = 1, North America = 0), past TNF exposure (Yes = 1, No = 0), Baseline value, and visit variables.
- Once the intermittent missing data are imputed, the monotone missing data will be imputed including covariates as defined above, based on the datasets created by the intermittent missing data MI. Since this dataset already has 100 imputed values at each visit, only 1 imputation will be performed.

## Step 2

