The dataset with the imputed results for each treatment arm will be combined into 1 complete dataset including each of the 100 imputations. If any imputed value is less than the lower limit of the allowable range for that parameter (as shown in Table 4-1), it will be changed to the lower limit of the range, and similarly for values higher than the allowable range. This dataset will be used to calculate the change from PA0008 Baseline variable where appropriate.

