### Step 3 (CRP only)

The CRP data will be presented using the geometric mean, 95% confidence interval (CI) for the geometric mean, median, Q1, Q3, minimum and maximum. The change from Baseline will be expressed as the ratio to Baseline in the summaries. The following approach will be applied:

- Following the MI procedure the ratio to Baseline will be calculated for any of the imputed values
- The natural logarithm of the absolute values and of the ratios to Baseline will be calculated
- The logged values will be summarized by treatment, visit and imputation
- The datasets will be combined using PROC MIANALYZE in order to get the mean and 95% CI estimates from the absolute values and ratios to Baseline (based on logged data) across imputations
- The estimates of the mean and 95% CI will be back-transformed to obtain the geometric mean and 95% CI on the original scale
- For the median, Q1, Q3, minimum and maximum the procedure outlined above for the other endpoints will be followed

As a sensitivity analysis, certain efficacy variables will be summarized based on observed data (see [Section 8](#)).

As a further sensitivity analysis for ACR and PASI responses, the response variables will be derived following MI of the individual components for ACR or following MI of the overall PASI score. The ACR and PASI responses will then be derived for each subject and each imputation (where each imputation is performed across all individual components for ACR) and the number and percentage of subjects with each ACR and PASI response in each imputation will be

calculated. The mean value (across imputations) for the percentage of subjects with each ACR or PASI response will be reported.

A similar approach will be followed for the calculation and summary of the number and percentage of subjects with normal HADS scores (defined as having HADS-D and HADS-A <8 at the same visit) based on the HADS-D and HADS-A values after MI.

Primary and sensitivity analyses are summarized in Table 4–2. All summaries presenting data following MI will include only visits from PA0009 EV onwards (although the MI procedure will incorporate data from both PA0008 and PA0009).

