### 5.1.1 Impact of COVID-19

A listing of all visits affected by COVID-19 will be presented based on the Enrolled Set including the visit, date of visit, relationship to COVID-19, impact category and a narrative (short description) of the event. This data will be summarized by treatment group at completion of PA0008, and overall for the ES for the following:

- Impact of COVID-19 for any reason
- Impact of COVID-19 for any reason by country

In addition, in order to assess the potential impact of COVID-19 on the collection and reporting of efficacy data a separate listing and summary will be presented to display missing data and data collected via an alternative modality (eg, phone, video call). For the purpose of these displays, missing data will be presented only for visits affected by COVID-19 (as reported on the dedicated eCRF page) ie, missing data at other visits and for other reasons will not be included.

The following efficacy assessments may be collected remotely:

- HADS
- HAQ-DI
- SF-36
- PGADA
- PtAAP
- PsAID-9

For visits conducted remotely (as reported on the dedicated eCRF page), it is not possible to assess MASES, PhGADA, BSA, PASI, LDI, TJC or SJC, and therefore these assessments will be missing at the specified visit. In addition, for any missed visit or a visit conducted remotely, the CRP assessment will also be missing. Such assessments will be considered to be missing as a result of COVID-19. For these visits, it will therefore not be possible to assess DAS28(CRP) and may not be possible to classify the subject as an ACR responder or nonresponder.

A listing will be presented showing each impacted visit based on the FAS. This will include the planned visit, the visit date, and details of the assessments conducted remotely and/or those missing as a result of COVID-19.

These data will be presented in a summary table by treatment group at completion of PA0008 and overall for the FAS.

For both the listing and the summary table, only visits at which efficacy assessments are scheduled will be included.

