If a subject has experienced an improvement, this measure will be positive. If a subject has experienced a worsening in their condition, this measure will be negative.

The PASI75, PASI90, and PASI100 responses will be 1 if there was at least 75%, 90%, and 100% (respectively) improvement from PA0008 Baseline in the PASI score, and 0 if there was less than the cut-off value. A PASI100 responder at a given visit is therefore also a PASI90 and a PASI75 responder.

If BSA affected by psoriasis (determined by the BSA palm method described in [Section 8.1.9](#)) is <3% at PA0008 Baseline (or BSA at PA0008 Baseline is missing) then the PASI response will be set to missing.

Summaries of PASI responses will be restricted to subjects with a BSA affected by psoriasis of  $\geq 3\%$  at PA0008 Baseline.

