One set of summaries will be produced for all of the above parameters using data following NRI (for binary endpoints) or MI (for continuous endpoints) as appropriate, as described in Section 4.2.1. For BSA the summary will be based on OC data only.

For each of the following variables, an additional set of summaries will be produced using OC data:

- ACR
- PASI
- MDA
- MASES
- LDI

For each of the following variables, an additional set of summaries will be produced after the response variables have been derived following MI of components:

- ACR
- PASI

Finally, for PASI, supplementary summary tables will be presented for the following based on the imputation rules described in Section 4.2.2:

- PASI response derived using LOCF
- PASI response derived based on the BSA observed at the corresponding visit

The summary tables for CRP will display the absolute value and ratio to PA0008 Baseline and will contain n, geometric mean (and 95% CI), median, first and third quartiles (Q1 and Q3), minimum and maximum. Any values for the ratio to PA0008 Baseline below 0.01 will be presented as <0.01 in the listing and summary table.

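### SAP Section 8 derives the MI sensitivity ACR and PASI responses from scores averaged over imputations, whereas Section 4.2.1 derives response in each imputation; read literally, Section 8 counts a subject with missing PASI as p^100 instead of p for PASI100

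*SAP*

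**What the plan says.** SAP Section 4.2.1 sets out the MI sensitivity analysis in full. The ACR components or the overall PASI score are imputed. Then "The ACR and PASI responses will then be derived for each subject and each imputation", the number and percentage of responders are calculated in each imputation, and "The mean value (across imputations) for the percentage of subjects with each ACR or PASI response will be reported".

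Section 8 describes the same sensitivity analysis with another rule: "The response endpoint will be re-derived and summarized based on the mean value (across multiple imputations) of the ACR component scores", or of the PASI total score, after imputation. Here the scores are averaged first and response is derived once.

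Section 8.3 lists the resulting tables for ACR and PASI: "an additional set of summaries will be produced after the response variables have been derived following MI of components". It mentions no averaging of scores.

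Three other rules matter for the size of the difference:
- Section 4.2.1, Step 1: "A total number of imputations will be 100".
- Section 4.2.1, Step 2, for an imputed value under the allowed range: "it will be changed to the lower limit of the range". Table 4-1 puts that limit at 0 for PASI.
- Section 8.1.10: "The PASI75, PASI90, and PASI100 responses will be 1 if there was at least 75%, 90%, and 100% (respectively) improvement from PA0008 Baseline".

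**The concern.** Both sections speak of a mean across imputations, but of different quantities: percentages in Section 4.2.1, scores in Section 8. The Section 8 rule works like single mean imputation. Each imputed subject becomes almost a certain responder or a certain nonresponder, depending on which side of the cut-off the average falls, and the uncertainty that MI is meant to carry is lost.

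This matters most for PASI. Section 4.2.2 says that PASI is known to be missing at some visits because the schedule once required it only when BSA at that visit was at least 3%. The subjects affected had little psoriasis left and are plausible PASI100 responders, yet NRI counts them as nonresponders. The MI analysis is one of the checks on that. If the Section 8 sentence is programmed, the check for PASI100 largely reproduces NRI and could be read as confirming it.

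**Working it through.** The plan states no figure for this analysis, so there is none to reproduce.

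**PASI100.** Inputs from the SAP: 100 imputations, PASI truncated below at 0, and response only if PASI = 0. Let p be the chance that one imputed PASI for a given subject is 0 after truncation. The documents do not give p, so a range is shown.

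- Section 4.2.1 rule: the subject contributes the share of the 100 values equal to 0, which is p in expectation.
- Section 8 rule: the mean of 100 non-negative values is 0 only if all are 0. For independent draws the chance is p^100.

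| p (Section 4.2.1) | p^100 (Section 8) |
|---|---|
| 0.50 | 8 × 10^-31 |
| 0.80 | 2 × 10^-10 |
| 0.90 | 3 × 10^-5 |
| 0.95 | 0.0059 |
| 0.99 | 0.366 |
| 0.999 | 0.905 |

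An even chance needs p = 0.5^(1/100) = 0.9931, and a 10% chance needs p = 0.1^(1/100) = 0.9772. If draws are roughly normal before truncation, the predicted PASI must lie 2.46 and 2.00 draw SDs below zero respectively. At 1 SD below zero, p = 0.84 and p^100 = 3 × 10^-8. The rounding to 12 decimals in Section 3.1 is too fine to turn a positive mean into 0 in practice.

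Independence is reasonable given multiple chains and a separate monotone draw per dataset. Positive dependence would raise the figure above p^100 but never above p.

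**Effect on a group percentage (assumed inputs).** Observed PASI100 rate 60%, 20% missing, p = 0.6:
- Section 4.2.1: 0.8 × 0.6 + 0.2 × 0.6 = 60%.
- Section 8: 0.8 × 0.6 + 0.2 × 0.6^100 = 48%, which is the NRI result.

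**PASI75 and PASI90 (assumed inputs).** Baseline PASI 8, draws normal with mean 1 and SD 2, truncated at 0. PASI75 needs a score of 2 or less; PASI90 needs 0.8 or less.
- Per imputation: Φ((2 − 1)/2) = 0.69 and Φ((0.8 − 1)/2) = 0.46.
- The expected truncated score is 1 × Φ(0.5) + 2 × φ(0.5) = 0.691 + 0.704 = 1.40. This is below 2 and above 0.8, so the mean-score rule gives about 1.00 for PASI75 and 0.00 for PASI90.

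Over a wider grid (baseline 6, 8 or 12; subject predicted means centred on 0 to 1.5 with spread 0.5 or 1.0; draw SD 1 to 2) the shift, Section 8 minus Section 4.2.1, among imputed subjects ran from −24 to +25 points for PASI75 and from −47 to +19 for PASI90.

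**ACR (assumed inputs).** Take ACR50 turning on one imputed component with draw SD 30 points, so the mean of 100 draws has SD 3.
- Mean improvement 60%: Φ(10/30) = 0.631 per imputation, against Φ(10/3) = 0.9996 from the mean.
- Mean improvement 40%: 0.369 against 0.0004.

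A seven-component simulation used normal percent improvements capped at 100, subject means centred on 30, 50 or 70 with spread 10 to 30, within-draw correlation 0 or 0.5, and draw SD 15 or 30. The ACR20 shift among subjects with the stated components imputed was:
- CRP only: 0 to +2.9 points.
- TJC, SJC, PhGADA and CRP: +0.5 to +42 points. This is the set lost at a remote visit; Section 5.1.1 says "it is not possible to assess MASES, PhGADA, BSA, PASI, LDI, TJC or SJC", and that CRP is missing too.

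Centred on 10%, the shift across all missing patterns was −4.9 to +15 points.

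**The case against.** The best reply is that the SAP already contains the right algorithm. Section 4.2.1 spells out every step, and Section 8 opens by pointing to it. Section 8.3, Protocol Section 13.8 and the SAP amendment summary all describe MI of component scores without averaging them. Table 4-2 footnote a derives response from the complete dataset, and Step 2 describes that dataset as holding each of the 100 imputations, so the footnote leans the same way. The Section 8 sentence may be a misplaced modifier, and a programmer may well follow Section 4.2.1.

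Most of this stands, and it shows which rule should be kept. It does not remove the conflict. The pointer in Section 8 covers how missing data are imputed; the section then states its own response rule, and nothing says which section prevails.

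Three limits on size also stand:
- p^100 is a per-subject probability. It applies only to subjects with BSA of at least 3% at PA0008 Baseline whose PASI is missing at the visit. Group rates move in proportion to the missing share.
- The ACR simulation draws percent improvements, whereas the SAP imputes absolute values within Table 4-1 limits. It does not represent skewed CRP or zero baselines.
- The remote-visit pattern cannot affect Week 48, because Section 8.5 says the pandemic began after all subjects had completed that visit.

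**Conclusion.** The concern holds, as a minor point. The two sections prescribe different algorithms for the same tables, and the Section 8 version gives a wrong result if followed. The p^100 result for PASI100 follows from the SAP's own rules plus independence of the draws. The PASI75, PASI90 and ACR figures rest on assumed inputs and show only that the shift can be large and can go either way. No general effect on the ACR tables is claimed, because the missing-data pattern is not given.

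The reach is narrow: the MI version of the by-visit ACR and PASI tables under Section 8.3. Section 8.2 plans only NRI and observed-case summaries for ACR and PASI. Those, the BSA-based and LOCF analyses of Section 4.2.2, the NRI-based maintenance and subgroup summaries, and the primary safety results are untouched.

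**What to change.** Replace the Section 8 sentence with the Section 4.2.1 rule, for example:

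> Response will be derived within each of the 100 completed datasets from the imputed ACR components or PASI total score, the responder percentage calculated in each, and the mean percentage across imputations reported (Section 4.2.1).

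The cost is one sentence of SAP text. No extra programming is needed if Section 4.2.1 is what is implemented. If the Section 8 sentence has been programmed, the MI response tables need to be re-derived.

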## 8.1 Derivation of efficacy variables

Derived efficacy variables at PA0008 Baseline will be taken from the PA0008 database. Derivations described below will only be performed for data in the PA0009 database (which includes PA0008 Week 48 relabeled as PA0009 EV).

For composite endpoints, component assessments will be combined based on the visit assignment following any mapping as described in [Section 3.5](#). Assessments from the same assigned visit will be used, regardless of actual assessment date.

### 8.1.1 78/76-joint evaluation for ACR response

The following joints are assessed for tenderness:

- Temporomandibular joints (x2)
- Sternoclavicular joints (x2)
- Acromioclavicular joints (x2)
- Shoulder joints (x2)
- Elbow joints (x2)
- Wrist joints (x2)
- Carpometacarpal joints of the thumb (x2)
- Metacarpophalangeal (MCP) joints of the hands (x10)
- Proximal interphalangeal (PIP) joints of the hands (x8) and interphalangeal (IP) joints of the thumbs (x2)
- Distal interphalangeal (DIP) joints of the hands (x8)
- Hip joints (x2)
- Knee joints (x2)
- Talotibial (ankle) joints (x2)

- Tarsal joints (x2)
- Metatarsophalangeal (MTP) joints of the feet (x10)
- PIP joints of the feet (x8) and IP joints of the big toes (x2)
- DIP joints of the toes (x8)

All, except for the hips, are assessed for swelling.

The swelling and tenderness grading criteria are summarized in [Table 8-1](#) .

**Table 8-1: Swelling and tenderness grading criteria**

Grade	Swelling response (76)	Tenderness response (78)
0	None	Not tender
1	Detectable synovial thickening with or without loss of bony contours, or bulging synovial proliferation with or without cystic characteristics	Positive response to questioning (tender), spontaneous response elicited (tender and winced) or withdrawal by subject on examination (tender, winced, and withdrew)

[Table 8-2](#) summarizes the joint categorization and derived tenderness and swelling categories at each visit.

**Table 8-2: Joint categorization and derived tenderness and swelling**

Joint Category		Swelling category	Tenderness category
-1	Missing/not recorded.	Missing	Missing
0	No symptoms.	0	0
1	Pain/tender only.	0	1
2	Swollen only.	1	0
3	Pain/tender and swollen.	1	1
4	Permanently not evaluable.	Missing	Missing
5	Temporarily not evaluable.	Missing	Missing
6	Injection.	1	1

For the purposes of calculating total tender and swollen joint counts, joints will be handled as follows:

- Category 4 joints will be considered missing for both tender and swollen joint counts at the visit at which the category was recorded and all subsequent visits. Joints in category 4 at any

time in PA0008 will be considered missing for both tender and swollen joint counts at all visits in PA0009.

- Category 6 joints will be considered tender and swollen at the visit at which the category was recorded and subsequent visits up to 364 days following the date of the visit. Joints that were in category 6 in PA0008 will be considered tender and swollen at all PA0009 visits up to 364 days following the date of the assessment in PA0008.

The TJC and SJC are weighted joint counts. If there are missing observations in the tender or swollen joint assessments, then the remaining observations will be assessed and weighted by the number of the assessed joints:

$$SJC = n * \sum_{i=1}^n SJ / \sum_{i=1}^n AJ \quad (11)$$

$$TJC = n * \sum_{i=1}^n TJ / \sum_{i=1}^n AJ \quad (12)$$

where n is the total number of joints, SJ is a swollen joint, TJ is a tender joint and AJ is an assessed joint.

If more than 50% of the planned tender joint assessments (ie, more than 39 assessments) or more than 50% of the planned swollen joint assessments (ie, more than 38 assessments) are missing at a visit, then the TJC or SJC will be set to missing for that visit.

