10 ASSESSMENT OF EFFICACY

Several assessments must be completed in order to determine the ACR response. These include the TJC and SJC based on 78 and 76 joints, respectively, PGADA, PhGADA, PtAAP, HAQ-DI, and CRP. The methods for the component measures will be described first, followed by ACR response and assessments used in secondary and other efficacy variables.

The timing for all assessments is specified in the schedule of study assessments (Table 5-1).

10.1 78/76 joint evaluation for ACR response

The Principal Investigator, another delegated physician, or an appropriately qualified medical professional (based on local requirements) who has had documented training on how to perform

these assessments correctly assesses the following joints for tenderness: the distal interphalangeal, proximal interphalangeal and metacarpophalangeal joints of the hands, and metatarsophalangeal joints of the feet, the carpometacarpal and wrist joints (counted separately), the elbows, shoulders, acromioclavicular, sternoclavicular, hip, knee, talo-tibial, and midtarsal joints. All of these except for the hips are assessed for swelling.

Artificial and ankylosed joints, as well as missing joints (ie, amputated joints), are excluded from both tenderness and swelling assessments.

One dactylitic digit is to be counted as 1 swollen joint (instead of counting as 3 in the finger or 2 in the toe).

Table 10–1 summarizes the swelling and tenderness grading criteria.

Table 10–1: Swelling and tenderness grading

Grade	Swelling response (76)	Tenderness response (78)
0	None	Not tender
1	Detectable synovial thickening	Tenderness present

10.2 28 joint evaluation for determination of DAS28(CRP)

The following 28 joints will be used for calculation of the DAS28(CRP).

- Upper extremity (26)-bilateral shoulders, elbows, wrists (includes radiocarpal, and carpal and carpometacarpal bones considered as a single unit), metacarpophalangeal (MCP) I, II, III, IV, and V, thumb interphalangeals (IP), proximal interphalangeal (PIP) II, III, IV, and V
- Lower extremity (2)-knees

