## 3 DATA ANALYSIS CONSIDERATIONS

### 3.1 General presentation of summaries and analyses

All computations and generation of outputs will be performed using SAS® Version 9.3 or later.

UCB uses SAS in a 64-bit Windows environment, and it is well-documented that in this environment the maximum accuracy of any numeric value is 15 significant digits. However, SAS by default does not limit the accuracy of numeric values to 15 significant digits which, in certain instances, may result in inaccurate representation of the data and cause errors when used in subsequent calculations, particularly when comparing a value to a chosen threshold. This, in turn, could potentially result in a change in classification of a subject from a responder to a nonresponder (and vice versa) if these values occur on a threshold used in the evaluation of response (or a critical laboratory value for example).

Therefore, in order to avoid issues caused by inaccurate floating point representation of numeric values, temporary variables are created (ie, for absolute values, change and percentage change from Baseline) during programming which are rounded to 12 decimal places prior to comparison to a specific threshold in the derivation of a response parameter. This does not imply inherent rounding on the ADaM variables AVAL (absolute value), CHG (change) or PCHG (percentage change) which are retained unrounded in the final ADaM dataset. Thus, rounding is applied exclusively during the derivation of new response parameters or critical value variables, and the rounded values are created on a temporary basis only.

All tables and listings will use Courier New font size 9.

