### 8.1.11 Minimal Disease Activity

Minimal disease activity is a state of disease activity deemed a useful target of treatment by both the patient and physician, given current treatment possibilities and limitations. Criteria have been developed to determine whether a patient has reached MDA based on key outcome measures in PsA.

MDA will be assessed using component assessments from the same analysis visit, ie, after applying any visit mapping as outlined in [Section 3.5](#). MDA will only be assessed for visits at which all assessments (with the exception of BSA and PASI, see below) were planned to be collected.

A subject will be considered as having MDA if 5 or more of the following 7 criteria are fulfilled:

- TJC $\leq$ 1
- SJC $\leq$ 1

- $PASI \leq 1$  or  $BSA \leq 3$
- $PtAAP \leq 15$ mm
- $PGADA \leq 20$ mm
- $HAQ-DI \leq 0.5$
- Tender enthesial joints  $\leq 1$

The following additional rules will be applied:

- PASI or BSA
  - The criteria “ $PASI \leq 1$  or  $BSA \leq 3$ ” will be considered to be met if either of the 2 subcriteria are satisfied, even if the other assessment is missing. Note that a separate rule (as defined below) is applied for subjects with BSA affected by psoriasis of  $<3\%$  at PA0008 Baseline.
  - The criteria “ $PASI \leq 1$  or  $BSA \leq 3$ ” will be considered as a missing component (for OC) if only 1 subcriterion is available and this does not meet the condition for MDA
  - A subject with BSA affected by psoriasis of  $<3\%$  at PA0008 Baseline will always be considered to have met the criteria “ $PASI \leq 1$  or  $BSA \leq 3$ ”. This is the case because PASI and BSA are not planned to be measured at post-Baseline visits for subjects with BSA  $<3$  at PA0008 Baseline. However, if for some reason, PASI or BSA are measured post-PA0008 Baseline for such subjects, and the results indicate a  $PASI > 1$  or  $BSA > 3$ , then this criterion will be considered as not having been met.
- The MASES items will be used to assess whether a subject has  $\leq 1$  tender enthesial joint: if the total derived MASES score is  $\leq 1$  then the criterion will be considered met.
- If any component is missing then the criteria for that component will be considered to have not been met.

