### 8.1.13 Maastricht Ankylosing Spondylitis Enthesitis Index

The MASES Index comprises six two-sided and one one-sided item (bilateral costochondral 1, costochondral 7, anterior superior iliac spine, posterior iliac spine, iliac crest and proximal insertion of the achilles tendon sites, and the fifth lumbar vertebral body spinous process) ([Heuft-Dorenbosch et al, 2003](#)) each scored as 0 = not tender or 1 = tender and then summed for a possible score of 0 to 13, with higher scores indicating worse enthesitis.

If 7 or more items are available, MASES will be calculated by dividing the summed score with the number of assessments and multiplying the result by 13. If less than 7 items are available, MASES will be treated as missing.

Summaries of MASES will be restricted to subjects with a MASES >0 at PA0008 Baseline.

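### The MDA joint cut-offs are tested on up-weighted counts, so a subject with a permanently non-evaluable joint and exactly one affected joint fails a criterion that the plain count meets

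*SAP*

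**What the plan says.** - **Joint counts.** SAP 8.1.1 says that "The TJC and SJC are weighted joint counts". If observations are missing, "then the remaining observations will be assessed and weighted by the number of the assessed joints" (equations 11 and 12), "where n is the total number of joints, SJ is a swollen joint, TJ is a tender joint and AJ is an assessed joint".
- **What counts as missing.** In SAP Table 8-2, unrecorded joints (category -1), permanently non-evaluable joints (category 4) and temporarily non-evaluable joints (category 5) are all missing. A category 4 joint stays missing at all later visits, and one recorded at any time in PA0008 is missing throughout PA0009.
- **Why some joints are never scored.** Protocol 10.1: "Artificial and ankylosed joints, as well as missing joints (ie, amputated joints), are excluded from both tenderness and swelling assessments".
- **MDA.** SAP 8.1.11: "A subject will be considered as having MDA if 5 or more of the following 7 criteria are fulfilled". Two of the seven are a tender joint count (TJC) and a swollen joint count (SJC) of no more than 1. Protocol Table 10-3 states the same two criteria as plain joint counts.
- **Rounding.** Under SAP 3.1, values are "rounded to 12 decimal places prior to comparison to a specific threshold". No whole-number rounding is specified for MDA.

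**The concern.** Scaling to the full joint set suits a percentage improvement or a change score, because it keeps visits with different numbers of assessed joints comparable. It does not suit an absolute limit of one joint. Once the denominator is short, no scaled value lies between 0 and the first value above 1. A limit of at most one then works as a limit of none.

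For an artificial, ankylosed or amputated joint there is nothing unobserved to estimate. The joint cannot be tender or swollen in the sense of the criterion, so scaling adds a fraction of a joint that does not exist. The subject has one affected joint, meets the criterion as the protocol states it, and is recorded as failing it. Because category 4 carries forward, this applies at every later visit at which one joint is affected.

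The planned summaries would not reveal it. The scaled count is not missing. With all seven components present, SAP Table 12-2 records non-achievement without the worst-case flag, so the nonresponder-imputation and observed-case summaries carry the same result. SAP Table 4-2 plans no multiple-imputation analysis of MDA.

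**Working it through.** **Inputs.** Total joints n = 78 (tender) and 76 (swollen, hips omitted), from the joint list in SAP 8.1.1. Equations 11 and 12: count = n × affected / assessed. MDA limits from SAP 8.1.11.

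**1. Reproduce the plan's own figures.** The listed joints sum to 14 + 10 + 10 + 8 + 8 + 10 + 10 + 8 = 78, or 76 without the two hips. The missing-data limit begins "If more than 50% of the planned tender joint assessments (ie, more than 39 assessments": 0.5 × 78 = 39, and 0.5 × 76 = 38 for swelling. Both agree with the SAP, so the denominators are confirmed.

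**2. Score for one affected joint.**

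| Joints not evaluable | TJC | SJC | At most 1? |
|---|---|---|---|
| 0 | 78/78 = 1.000 | 76/76 = 1.000 | yes |
| 1 | 78/77 = 1.013 | 76/75 = 1.013 | no |
| 2 | 78/76 = 1.026 | 76/74 = 1.027 | no |
| 10 | 78/68 = 1.147 | 76/66 = 1.152 | no |
| most allowed (39 / 38) | 78/39 = 2.000 | 76/38 = 2.000 | no |

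Every denominator below the full set gives a value above 1. Rounding to 12 decimals leaves 1.012987012987 and 1.013333333333, so it does not help. A non-evaluable hip shortens the TJC denominator only.

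**3. Score for no affected joint.** 78 × 0/77 = 0 and 76 × 0/75 = 0. Both criteria are met.

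**4. Consequence for MDA (at least 5 of 7).** At most two criteria, TJC and SJC, can be lost this way.
- 5 met on plain counts: losing one or both gives 4 or 3, so MDA is lost.
- 6 met: losing one leaves 5 (MDA kept); losing both leaves 4 (MDA lost).
- 7 met: losing both leaves 5, so MDA is kept.

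**5. An example from the plan's own rules.** SAP 8.1.1 scores an injected joint (category 6) as tender and swollen for up to 364 days. Take one injected non-hip joint, one category 4 non-hip joint and no other active joint. TJC = 78/77 and SJC = 76/75, so both criteria fail, and MDA then needs all five others. Without the category 4 joint both counts are exactly 1 and both criteria are met.

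**The case against.** **SAP 8.1.11 does not itself say that its counts are weighted.** True, and a programmer might use raw counts. But SAP 8.1.1 gives the only definition of the 78/76-joint TJC and SJC, and the 28-joint counts of SAP 8.1.2 serve DAS28(CRP). Read as written, the weighted count applies.

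**For skipped or temporarily non-evaluable joints the true count is unknown.** This stands. The unobserved joint may be affected, so scaling is a prespecified estimate there. The error can be shown only for category 4 joints.

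**Enthesitis.** A reader might infer the same error for MASES. SAP 8.1.11 does use the derived score, and under SAP 8.1.13 "MASES will be calculated by dividing the summed score with the number of assessments and multiplying the result by 13", so one tender site out of 12 gives 13/12 = 1.083. However, SAP 8.1.13 has no class of permanently non-evaluable entheses. A missing site is simply unobserved, and misclassification is not shown.

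**The observed-case summary does not always carry the failure.** Correct. If another component is missing and four of the remaining six criteria are met, Table 12-2 applies the worst-case flag and the record leaves that summary.

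**Importance.** MDA is one of the other efficacy variables in a descriptive open-label study whose primary objective is safety. No primary or secondary variable is affected, and the bias runs against the drug. All of this stands and limits the weight of the point.

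**Conclusion.** The point holds for category 4 joints. Followed exactly, the SAP makes a subject with at least one such joint in the relevant count and exactly one tender or swollen joint fail a criterion that the protocol's plain count meets. That follows from the SAP's own equations and needs no assumption beyond reading TJC and SJC in 8.1.11 as defined in 8.1.1.

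The size of the effect on the MDA rate cannot be computed: the documents give neither the number of subjects with category 4 joints nor the number with a count of exactly one. It can only lower the rate. As illustration only, suppose 5% to 20% of subjects have such a joint and the MDA rate among them falls by 3 to 6 points. The latter range comes from a simple simulation that assumed 8% to 15% of them at a raw count of exactly one on each measure, correlated components and a true MDA rate of about 45%. The overall rate then falls by 0.05 × 3 = 0.15 to 0.20 × 6 = 1.2 points. With at most 200 subjects, that is 0.3 to 2.4 subjects. None of these inputs is in the documents.

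Two further readings are not supported. Subjects with no affected joint are not harmed. Nor do the documents show that the error concentrates in long-standing disease; they identify only joints that cannot be scored.

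**What to change.** Add one sentence to SAP 8.1.11: for the MDA joint criteria, category 4 joints are dropped without up-weighting. In equations 11 and 12 this means replacing n, for MDA only, by n minus the number of category 4 joints. If only category 4 joints are missing, the result is the observed count, which is then compared with 1. Keep the category 6 rule, the rule for more than 50% missing, and the weighted counts for ACR, DAS28(CRP) and change scores. Scaling for temporarily missing joints and for MASES can stay.

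Two alternatives are worse:
- **Treating the component as missing whenever unobserved sites could change the answer.** SAP 8.1.11 counts a missing component as not met. A subject with no observed active joint and two temporarily missing joints now scores 0 and passes; under this rule the subject would fail.
- **Rounding the weighted count to a whole number.** One affected joint would then pass only with at least 53 of 78 (78/53 = 1.47) or 51 of 76 (76/51 = 1.49) joints assessed.

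The cost is that sentence, a small programming change and a footnote, because MDA would use a slightly different joint count from ACR. No new data are needed.
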